9.3 Primary endpoint analysis

The primary endpoint analysis will only include patients from Cohort A.

Non-parametric survival analysis will be used to calculate the mortality rate at 1 year post index procedure and build its 95% confidence limit. The corresponding variance will be computed using Peto's formula for survival analysis. The survival time will be calculated as the number of days between the implant date and the death date for the patients who die at 1 year (365 days) post implant. And for the patients who are considered as censored (loss to follow up, explanted, etc.), the survival times will be calculated as the number of days between the implant date and the last known adverse event or the last documented contact date before 1 year follow up. A Kaplan-Meier curve with the cumulative survival rate will also be presented.

A Cox regression model can be used for further explanatory analysis of the relationship of the prognostic factors and the mortality. These factors will include baseline factors such as age, gender, NYHA class etc., and other factors defined by steering committee can also be analyzed.

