Adverse device effect that has resulted in any of the consequences characteristic of a serious adverse event.

Unanticipated Serious Adverse Device Effect (USADE)

A serious adverse device effect which by its nature, incidence, severity or outcome has not been identified in the current version of the risk analysis report.

Anticipated Serious Adverse Device Effect (ASADE)

A serious adverse device effect which by its nature, incidence, severity or outcome has been previously identified in the risk analysis report.

Device Deficiency (DD)

An inadequacy of a medical device with respect to its identity, quality, durability, reliability, safety or performance. Device Deficiencies include malfunctions, use errors and inadequate labeling.

7.3.2. Procedure for assessing, recording and reporting adverse events, adverse device effects, serious adverse events, serious adverse device effects and device deficiencies

Safety surveillance and reporting will be done for all patients enrolled in this investigation.

Safety surveillance within this clinical investigation and safety reporting, both performed by the investigator, starts as soon as the patient is enrolled in this clinical investigation (date of signature of the informed consent). The safety surveillance and the safety reporting will continue until the last investigational visit has been performed or the patient is deceased or the patient/investigator concludes his participation into the clinical investigation.

NOTE: If an adverse event is documented at the patient's last follow up visit, both the notification and follow-up information on the AE eCRF are to be provided to the sponsor.

- All Serious Adverse Events (regardless of their relationship with the device or the procedure) and all Adverse Device Effects (serious or non-serious) are to be documented and reported to the sponsor maximum 3 calendar days after becoming aware of the event.
- All Device Deficiencies, that could have led to a Serious Adverse Device Effect,
 - if either suitable action had not been taken;
 - if intervention had not been made or
 - if circumstances had been less fortunate,are to be documented and reported to the sponsor maximum 3 calendar days after becoming aware of the event.
- Non-serious adverse events documentation and reporting are limited to cardiovascular and neurovascular events; they all have to be reported regardless of their relationship with the device or the procedure.

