7.4 Patient Death

7.4.1. Procedure for recording and reporting Patient Death

7.4.2. All patient deaths are to be documented and reported to the sponsor maximum 3 calendar days after becoming aware of the event. Should death occur, the investigator is requested to record death information in the hospital records and immediately document the information on the Death Form. By completing the form the sponsor will be notified. Refer to

and Appendix C: Data Collection Method. In case of EDC failure, notify Sponsor via Fax or via [contact].

All efforts (including use of national death registries) should be made to identify, precisely characterize, and appropriately classify any death.

Patient death is an outcome of a serious adverse event (SAE). All efforts to get SAE details should be made and the Adverse Event eCRF must be completed.

If available, the explanted Portico valve should be returned to SJM per instructions provided in Appendix K: Explant, Return, and Analysis of Valve and Appendix L: Instructions for device return - Large and Small Kits.

The patient's death is an early conclusion of the patient's participation in the investigation. Therefore, the investigator is requested to complete the termination form. The investigator must notify the EC/IRB, if appropriate, in accordance with national and local laws and regulations.

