7.5 Criteria and procedures for patient withdrawal or discontinuation

Each patient should remain in the investigation until completion of the required follow up period; however, a patient's participation in the investigation may be discontinued. Should this occur, the reason for discontinuation must be documented in the source documents.

Patients must be informed about their right to withdraw from the investigation at any time and for any reason without sanction, penalty or loss of benefits to which the patient is otherwise entitled and withdrawal from the investigation will not jeopardize their future medical care or relationship with the investigator. Patients will be asked to specify the reason for the termination, but have the right not to answer.

The investigator may decide to withdraw a patient from the investigation at any time.

The patient's future care will not be influenced by a decision, voluntary or otherwise, to withdraw from the investigation. All reasonable efforts should be made to retain the patient in the clinical investigation until completion of the investigation.

Reasons for patient's withdrawal include, but are not limited to:

- Patient refuses to continue participating in the investigation (refuse all subsequent testing/follow up)
- Patient does not meet the inclusion/exclusion criteria prior to baseline procedure
- Patient is deceased (cause must be documented)
- Patient's non-compliance
- Patient's participation is terminated by the PI or investigator, although the patient consented, since participation is no longer medically justified
- Patient is 'lost to follow up': Patient does not adhere to the scheduled follow up visits but has not explicitly requested to be withdrawn from the clinical investigation. (This does not apply to missed visits). Site personnel should at all times make all reasonable efforts to locate and communicate with the patient in order to achieve patient compliance to the scheduled follow up visits. A patient will be considered 'lost to follow up' after
 - A minimum of 2 phone calls from a physician or delegate at the investigational site have been attempted to reach the patient. These 2 phone calls need to be documented in the patient's hospital records.
 - And a certified letter has been sent to the patient's last known address or general practitioner (GP). A copy of this letter should be maintained in the patient's hospital records. If these attempts are unsuccessful,

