9.4 Secondary endpoint analysis

The secondary endpoint analysis will include both cohorts but results will be presented separately.

All safety secondary endpoints will be estimated using non-parametric survival analysis, and the data will be presented with the aid of Kaplan-Meier curve. The time to event will be defined as from the implant date to the first occurrence of the event for the patients who experienced the event, or to the last documented contact date for the patients without the event.

All safety secondary endpoints will be reported at 30 days, 1 year, 2 years, 3 years, 4 years and 5 years post implant, as recommended by VARC 2.

Note: Safety events which occurred prior to the index procedure will be reported separately and will not be included in the safety secondary endpoints reporting.

All continuous secondary endpoints will be summarized with the number of non-missing data, mean \pm standard deviation, median and range (minimum – maximum).

All categorical secondary endpoints will be tabulated with number of occurrence, and the percentage.

Generalized linear mixed model will be used to assess the evolution of the NYHA class at baseline, 30 days, 1 year, 2 years, 3 years, 4 years and 5 years post implant.

General linear mixed model will be used to evaluate the improvement for the QOL at baseline, 30 days, 1 year, 2 years, 3 years, 4 years and 5 years post implant.

Other secondary endpoints analysis will be described in a separate statistical analysis plan. This document will be available upon request.

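### Section 9.3 treats explant as a reason to censor 1-year all-cause mortality and gives two censoring dates where section 9.4 gives one; a minor fault that a wording change cures

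*Combined protocol and SAP*

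**What the plan says.** Section 5.3.1 makes all-cause mortality at 1 year after implant the primary endpoint. Section 9.3 estimates it in Cohort A by non-parametric survival analysis and sets two timing rules.

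- **Deaths:** time runs from implant to "the death date for the patients who die at 1 year (365 days) post implant".
- **Censored patients:** "for the patients who are considered as censored (loss to follow up, explanted, etc.), the survival times will be calculated", ending at "the last known adverse event or the last documented contact date before 1 year follow up".

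Section 5.3.2 lists all-cause mortality at 1 year again, as a secondary endpoint. Section 9.4 analyses the safety secondary endpoints in both cohorts, presented separately. It ends time at the first event "or to the last documented contact date for the patients without the event". It names no explant rule and no adverse-event date.

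On follow-up, section 7.5 says "Each patient should remain in the investigation until completion of the required follow up period". Explant is not among its withdrawal reasons, although that list is open and "The investigator may decide to withdraw a patient from the investigation at any time". Safety reporting under section 7.3.2 runs "until the last investigational visit has been performed or the patient is deceased or the patient/investigator concludes his participation into the clinical investigation". On deaths, section 7.4 says: "All efforts (including use of national death registries) should be made to identify, precisely characterize, and appropriately classify any death".

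**The concern.** Loss to follow-up ends observation. Explant does not: the patient can still be followed, and the rest of the plan expects that. If a patient leaves the study after an explant, the exit is the reason for censoring, not the explant.

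Two things follow from naming explant as a censoring reason. A death after explant could be left out of an all-cause count, or an explanted survivor's observed time could be cut short. Either would be informative censoring if explanted patients differ in risk. The text does not say which of the two timing rules governs a patient who is explanted and then dies by day 365.

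The censoring date raises a separate problem. Two analysts could follow section 9.3 faithfully and censor the same lost patient on different days, and section 9.4 could give a third result. This figure is the trial's main estimate and, under section 5.3.2, may be set against an external comparator for reimbursement agencies. It should have one reproducible definition.

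**Working it through.** **Inputs from section 9.2.1:** 1-year mortality 22.1%, so survival S = 0.779; 608 at risk at 1 year; limits 18.8% to 25.4%; dropout 10%; 866 recruited.

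**The plan's own figures.**
- At risk: 1.96² × 0.779 × 0.221 / 0.033² = 607.3, stated as 608.
- Half-width: 1.96 × √(0.779 × 0.221 / 608) = 0.0330, or 3.3 points.
- Recruited: 607.3 / (0.779 × 0.9) = 866.2, stated as 866.

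These reproduce, and the point below does not change them.

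**Assumptions.** The documents give no explant rate, no mortality after explant and no contact dates. I fix true 1-year mortality at 22.1% and use two time patterns: a constant hazard, and 30% of the year's deaths by day 30 (survival at day 30 = 1 - 0.3 × 0.221 = 0.9337). Ranges span both. Shifts are in percentage points of estimated mortality.

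**1. Explant.** Let a fraction e be explanted at day 30, of whom a proportion p die by day 365. The other patients' mortality is set so that the total stays at 22.1%, and s is overall survival at day 30. If explanted patients are all censored at explant, Kaplan-Meier survival at day 365 is

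s × [0.779 - e(1 - p)] / (s - e).

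- e = 1%, p = 50%, early-death pattern (s = 0.9352): 0.9352 × 0.774 / 0.9252 = 0.7824, a shift of -0.34.
- e = 1%, p = 15%, constant hazard (s = 0.9798): 0.9798 × 0.7705 / 0.9698 = 0.7784, a shift of +0.06.
- e = 0.2% (about 2 of 866), p = 15% to 50%: +0.01 to -0.07.

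If deaths after explant count but explanted survivors are still censored at day 30, the denominator becomes s - e(1 - p). With e = 1% the shift is then +0.08 to +0.18. If explanted patients are carried to day 365, it is zero.

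**2. Censoring date.** Let a fraction d be due to be lost, with last contact on day L and last adverse event on an earlier day A. Deaths before loss still count. Censoring at A instead of L changes estimated survival from 0.779 to

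0.779 × (1 - d) / [1 - d × S(L)/S(A)].

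The visit schedule limits L. The pre-discharge visit is by day 7. The 30-day visit has a window of -7 to +14 days, so it ends at day 44. The 1-year visit has a window of ±90 days, so it opens at day 275. No scheduled visit lies between day 44 and day 275. A patient lost after the 30-day visit would therefore usually have a last contact around day 30 to 44. I take A from day 7 to day 30.

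- Largest case: A = 7, L = 44, early-death pattern. S(44)/S(7) = 0.9267/0.9841 = 0.9416.
- d = 10%: 0.779 × 0.9 / (1 - 0.09416) = 0.7740, a shift of +0.50.
- d = 5%: 0.779 × 0.95 / (1 - 0.04708) = 0.7766, a shift of +0.24.
- d = 2%: 0.779 × 0.98 / (1 - 0.01883) = 0.7781, a shift of +0.09.
- Any d, if the two dates coincide: zero.

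**3. Sections 9.3 and 9.4 side by side.** In Cohort A at 1 year, the former may end a lost patient's time at an adverse event and may censor at explant. The latter uses last documented contact and is silent on explant. The same data can therefore give two figures for one quantity.

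**The case against.** The strongest reply is that ordinary usage settles the matter. One rule covers patients who die. The other covers patients who are censored, which in survival analysis means those without the event, and section 9.4 makes that split openly. On that reading every known death counts. This is plausible, but section 9.3 does not say it, and explanted survivors would still be listed as censored.

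A second reply is that ending follow-up at explant describes a legitimate target, mortality while the valve is in place. Section 5.3.1 does not define that target; it says all-cause mortality at 1 year.

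A third is that with so few visits an adverse event may be later than the last visit, so naming both dates may be meant to extend follow-up. That is reasonable, and it is what a later-of-the-two rule would secure.

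Sections 9.1 and 9.4 mention a separate statistical analysis plan, for eligibility deviations and for other secondary endpoints. Section 9.3 does not defer to it on primary-endpoint censoring.

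The objection on size stands. A reader might infer that the date choice alone could cost 0.67 to 1.54 points at 10% lost. The formula gives those values only if last contacts fall on days 180 to 300, which the visit schedule does not support without unscheduled contacts. A shift of about -1.0 from explant needs 3% explanted and 50% of them dying; the documents support neither figure.

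**Conclusion.** The point holds as a minor fault of specification. Explant does not belong among the censoring reasons for an all-cause mortality endpoint, and sections 9.3 and 9.4 should not define the same Cohort A figure differently.

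The size is illustrative, because every rate and date beyond the plan's 22.1% and 10% is assumed. Censoring at explant gives +0.06 to -0.34 points at 1% explanted, and less than 0.1 at 0.2%. The date choice gives 0 to +0.50 points at 10% dropout and 0 to +0.24 at 5%, with more only if lost patients have later unscheduled contacts. Against a half-width of 3.3 points these are small. The effects can run in opposite directions, so the net direction is unknown. The analysis is a single-arm estimate with no hypothesis test or performance goal, so no formal conclusion could reverse.

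A reader might infer that the plan discards deaths after explant. The documents do not establish that; they only leave it open.

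**What to change.** In section 9.3, delete explant from the censoring reasons and state:

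*Every death from implant to day 365 is an event on its date, including after explant. Patients known alive at or beyond day 365 are censored at day 365. All others are censored at the latest date known alive, which is the later of the last documented contact and the last adverse event.*

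Use the same rule for 1-year all-cause mortality in section 9.4.

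No rule on registry completeness is needed for this. If registries are searched for lost patients, a sensitivity analysis with and without deaths known only from a registry is optional.

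The cost is one paragraph of text. There are no extra patients, visits or procedures, and 608 and 866 stay as they are.

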9.4 Secondary endpoint analysis

The secondary endpoint analysis will include both cohorts but results will be presented separately.

All safety secondary endpoints will be estimated using non-parametric survival analysis, and the data will be presented with the aid of Kaplan-Meier curve. The time to event will be defined as from the implant date to the first occurrence of the event for the patients who experienced the event, or to the last documented contact date for the patients without the event.

All safety secondary endpoints will be reported at 30 days, 1 year, 2 years, 3 years, 4 years and 5 years post implant, as recommended by VARC 2.

Note: Safety events which occurred prior to the index procedure will be reported separately and will not be included in the safety secondary endpoints reporting.

All continuous secondary endpoints will be summarized with the number of non-missing data, mean \pm standard deviation, median and range (minimum – maximum).

All categorical secondary endpoints will be tabulated with number of occurrence, and the percentage.

Generalized linear mixed model will be used to assess the evolution of the NYHA class at baseline, 30 days, 1 year, 2 years, 3 years, 4 years and 5 years post implant.

General linear mixed model will be used to evaluate the improvement for the QOL at baseline, 30 days, 1 year, 2 years, 3 years, 4 years and 5 years post implant.

Other secondary endpoints analysis will be described in a separate statistical analysis plan. This document will be available upon request.

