5.3.2 Secondary Endpoints

- Evaluation of the VARC-2¹⁹ defined event rates at 30 days, 1 year and annually through 5 years post implant. Definitions are detailed in Appendix D: VARC 2 Endpoints Definitions.
 - All-Cause Mortality
 - Cardiovascular Mortality
 - Myocardial Infarction
 - Stroke (disabling and non-disabling)
 - New or worsened conduction disturbances and cardiac arrhythmias (including pacemaker implantation rate at 30 days and new-onset atrial fibrillation (AF))
- Evaluation of the VARC-2¹⁹ defined event rates at 30 days from the index procedure.
 - Vascular access site complication (major and minor)
 - Bleeding (life-threatening, major and minor)
 - Acute kidney injury

- Prosthetic valve function at 30 days, 1 year and annually through 5 years post implant. (Includes prosthetic valve stenosis and prosthetic valve regurgitation).
- Clinical benefit endpoints at 30 days, 1 year and annually through 5 years post implant (if available)
 - NYHA functional classification
 - 6 Minute Walk Test (6MWT)
 - Quality of life measured with EQ-5D questionnaire through 1 year post-implant
- Evaluation of the TAVI-related resource utilization through hospital discharge (e.g. index procedural hospital/physician resources)
- Interim reporting at 30 days and 1-year all-cause mortality data may be performed on a subset of patients and compared with an appropriate external comparator. The results will be presented to appropriate agencies in France and in other countries where it will be deemed necessary for reimbursement purposes.

NOTE: Should new VARC or ESC Guidelines be published, endpoint analysis would be adjusted accordingly and analyzed to the extent that the previously gathered data supports the analyses based on the most current guidelines.

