9.2 Sample size estimation

9.2.1 Cohort A

The sample size estimation is based on the primary endpoint of this study, all-cause mortality at 1 year post implant for patients having received a Portico Valve.

It is assumed that the expected mortality rate at 1 year post implant will be 22.1% ²⁰), and the total recruitment period will be 2 years; at least 608 patients are required to be at risk at 1 year post implant, in order to establish a two sided 95% confidence limit (18.8%, 25.4%) using non-parametric survival analysis with Peto's variance²¹. With a dropout rate of 10%, at least 866 patients need to be recruited.

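### Section 9.4 gives no rule for death as a competing event, so if late Kaplan-Meier event rates are read as the share of patients affected, they are too high for stroke, MI and cardiovascular death

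*Combined protocol and SAP*

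**What the plan says.** Section 9.4 sets one method for the whole group: "All safety secondary endpoints will be estimated using non-parametric survival analysis, and the data will be presented with the aid of Kaplan-Meier curve". Time runs from implant to the first event, "or to the last documented contact date for the patients without the event". On timing it adds: "All safety secondary endpoints will be reported at 30 days, 1 year, 2 years, 3 years, 4 years and 5 years post implant". Both cohorts are analysed and presented separately. Only other secondary endpoints are left to a separate statistical analysis plan, which is not among the documents.

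Section 5.3.2 asks for VARC-2 "defined event rates at 30 days, 1 year and annually through 5 years post implant". The list under it is all-cause mortality, cardiovascular mortality, MI, stroke, and new or worsened conduction disturbances and arrhythmias. The Synopsis puts the arrhythmia item in a bullet of its own, where the only time given is 30 days, for the pacemaker rate.

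Death is handled explicitly elsewhere. For the primary endpoint, section 9.3 says: "The survival time will be calculated as the number of days between the implant date and the death date". Section 7.5 includes among the reasons for withdrawal: "Patient is deceased (cause must be documented". Section 7.4.1 requires: "All efforts (including use of national death registries) should be made to identify, precisely characterize, and appropriately classify any death". None of these sections, nor 9.4, names death as a competing event for the other safety endpoints.

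**The concern.** A patient who dies without a stroke is a patient without the event. Under 9.4 that patient leaves the risk set at last contact, exactly like someone who moved away. Kaplan-Meier then treats the dead patient as still able to have a stroke later. One minus Kaplan-Meier is a legitimate estimate of risk as if other deaths did not occur. It is not the proportion of implanted patients who have the event, which is how most readers would take an event rate. When event-free deaths are censored it can only be equal to or above that proportion, and the gap widens as deaths accumulate.

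The competing risk here is not small: section 9.2.1 assumes 22.1% dead at 1 year, and follow-up runs to 5 years. What is at stake is the late descriptive rates of stroke, MI and cardiovascular death, and possibly arrhythmia. For these endpoints the estimates are the entire result.

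**Working it through.** **The plan's own figure.** Section 9.2.1 takes 22.1% mortality at 1 year and limits of 18.8% to 25.4%, a half-width of 3.3 points. The number at risk is 1.96² × 0.779 × 0.221 / 0.033² = 607.3, against 608 stated. Enrolment is 607.3 / 0.779 / 0.90 = 866.2, against 866 stated. So 22.1% is the working mortality assumption, and these sample-size figures do not depend on the present point.

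**Inputs.** From the documents: 22.1% dead at 1 year, a death hazard of −ln(0.779) = 0.2497 in year 1. Assumed: later mortality m of 5%, 10% or 22.1% a year (hazard −ln(1−m)), giving 36.6%, 48.9% or 71.3% dead at 5 years. Event patterns and the cardiovascular share of deaths are also assumed.

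**Formulas.** With event hazard h, cumulative event hazard H and cumulative death hazard D:
- One minus Kaplan-Meier, event-free deaths censored: 1 − exp(−H).
- Cumulative incidence, the share affected: integral of h·exp(−H − D).

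**One case by hand** (3% by 30 days, then 1% a year; m = 22.1%):
- One minus Kaplan-Meier at 5 years: 1 − 0.97 × exp(−0.01 × 4.918) = 7.65%.
- To 30 days the event hazard is −ln(0.97) / (30/365) = 0.3706. Incidence is 0.3706/0.6203 × (1 − exp(−0.6203 × 0.0822)) = 2.97%, and 95.03% remain alive and event-free.
- After that: 0.9503 × 0.01/0.2597 × (1 − exp(−0.2597 × 4.918)) = 2.64%.
- Sum 5.61%; 7.65 / 5.61 = 1.36.

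**Results at 5 years** (ranges run from m = 5% to m = 22.1%):

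| Assumed pattern | 1 − KM | Cumulative incidence | Relative excess |
|---|---|---|---|
| 3% by 30 days, then 1% a year | 7.65% | 6.40-5.61% | 20-36% |
| 3% by 30 days, then 2% a year | 12.09% | 9.68-8.15% | 25-48% |
| 10% by 30 days, then 1% a year | 14.32% | 13.08-12.35% | 9-16% |
| 10% by 30 days, none later | 10.0% | 9.9% | about 1% |

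In the first pattern the excess is about 1% at 30 days, 4% at 1 year, 8-10% at 2 years and 12-18% at 3 years.

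**Cardiovascular death**, as a constant share s of all deaths: one minus Kaplan-Meier is 1 − exp(−sD) and cumulative incidence is s(1 − exp(−D)), with D = 0.455 to 1.249 at 5 years.
- s = 80%: 30.5-63.2% against 29.2-57.1%, an excess of 4-11%.
- s = 60%: 23.9-52.7% against 21.9-42.8%, an excess of 9-23%.

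**Fatal events.** Appendix D counts some deaths as MI or stroke, and these do not compete. If they are 10-20% of deaths (assumed), the first three table rows fall to 16-33%, 20-44% and 8-15%.

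**Against sampling error.** With 866 patients and no loss to follow-up, the Kaplan-Meier 95% half-width at 5 years is 2.0-2.3, 2.5-2.9 and 2.5-2.7 points in the first three rows. The bias is 1.3-2.0, 2.4-3.9 and 1.2-2.0 points.

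**The case against.** **The estimand is unstated, not wrong.** Section 9.4 never says the curves estimate the share of patients affected, and 5.3.2 does not define its event rates. A reader might infer that the planned late rates are simply incorrect. The documents do not support that: the method is valid for a different quantity. This stands, and the point is conditional on the reading.

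**Arrhythmia may hardly be affected.** A reader might infer the same bias for new conduction disturbance or arrhythmia. The Synopsis gives that endpoint no annual times although 5.3.2 does, and Table 2 stops scheduled ECGs at 1 year. If nearly all events fall by 30 days, the excess is about 1%. This also stands.

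**The size is mostly assumed.** True: only the 1-year mortality is given, and the top of each range needs 22.1% mortality every year. Appendix D classes deaths of unknown cause as cardiovascular, which favours high cardiovascular shares and the smaller bias. The direction does not depend on these assumptions. Nor does the bias shrink with more patients, although it often lies within the sampling error.

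**Other parts of the plan may cover it.** Section 9.4 also tabulates categorical endpoints by count and percentage. If that includes safety events, which it does not say, the gap would be partly visible. The separate analysis plan could add a rule, so one cannot say that none exists anywhere. But 9.4 itself already fixes the estimator for safety endpoints.

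**Conclusion.** The point holds in a conditional form. As 9.4 is written, event-free deaths are in effect censored. Read as the share of patients affected, the late rates of stroke, MI and cardiovascular mortality would then be too high, more so each year. The 5-year excess is about 20-48% relative for an endpoint with 3% by 30 days then 1-2% a year, and 4-23% for cardiovascular death at a 60-80% share. For arrhythmia it runs from about 1% to 9-16%, depending on how many events come after 30 days. These sizes rest on assumed later mortality of 5-22.1% a year and on assumed event patterns; the direction is certain.

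A reader might extend this to the main result. That would be mistaken. The primary endpoint and all-cause mortality have no competing event, the sample size does not change, and 30-day results move by about 1% relative. The study is single-arm, no test on these endpoints is stated, and the one external comparison named in 5.3.2 is on all-cause mortality. This is a worthwhile improvement with limited stakes.

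**What to change.** In 9.4, for safety endpoints reported beyond 30 days other than all-cause mortality, state for Cohort A that:
- cumulative incidence is estimated by the Aalen-Johansen estimator;
- death before the event is the competing event, dated at the death date (for cardiovascular mortality, non-cardiovascular death);
- deaths that Appendix D defines as the endpoint itself count as events;
- only patients alive and event-free are censored at last contact.

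Cohort B needs its own sentence. Under section 6.1.2 and the notes to Table 2, these patients enter at 1 year or later, as survivors, and their earlier data are not re-collected. Either use the same estimator with delayed entry at enrolment, conditional on being alive and event-free then, or combine it with the earlier trial data if those are available. It should not be run from implant as if they had been at risk from day 0.

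Also reconcile the Synopsis with 5.3.2 on whether arrhythmia is reported annually. Keep Kaplan-Meier for all-cause mortality and, if wanted, as a supplement.

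The cost is wording in 9.4 and the separate analysis plan, and a different option in standard software. Cohort A needs no new data, because 7.4.1 already has deaths recorded and classified. The small downside is that both estimates may have to be shown.
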